16.1.2 TEAEs leading to Discontinuation / Dose Reduction of Treatment

An overall summary table will present the number of subjects with at least one of the following, summarized by treatment arm:

- TEAE leading to temporary discontinuation of study drug
- Study drug related TEAE leading to temporary discontinuation of study drug
- TEAE leading to permanent discontinuation of study drug
- Study drug related TEAE leading to permanent discontinuation of study drug
- TEAE leading to study termination

The above listed summaries will also be presented for AESIs.

The following frequency tables will be prepared by treatment arm, primary SOC in alphabetical order, PT in order of decreasing frequency across both treatment arms and worst grade:

- TEAEs leading to temporary discontinuation of study drug
- TEAEs leading to permanent discontinuation of study drug
- Study drug related TEAEs leading to permanent discontinuation of study drug
- TEAEs leading to study termination
- TEAEs leading to death.

16.2 Deaths, Other Serious Adverse Events, and Other Significant Adverse Events

16.2.1 Deaths

Adverse events leading to death and treatment-related TEAEs leading to death will be summarized by primary SOC and PT, see Section 16.1.1.

The number of deaths and primary reason for death will be summarized based on the Death eCRF page by treatment arm. Also a listing of deaths for each treatment received will be provided including first and last dose date. In addition, a listing of TEAEs leading to death will be provided.

16.2.2 Serious Adverse Events

A separate listing will be provided of the subset of events indicated as serious. Serious TEAEs will also be summarized by primary SOC and PT, see Section 16.1.1.

16.2.3 Other Significant Adverse Event

16.2.3.1 Adverse Events of Special Interest (AESIs)

The occurrence of treatment-emergent adverse events of special interest (hypersensitivity) up to Week 52 is the primary endpoint (see Section 15.1 for the analysis of these AEs).

The following is considered pre-defined AESI for this study:

Hypersensitivity (defined by Standardized MedDRA Query [SMQ] narrow as per the latest MedDRA version).

16.3 Clinical Laboratory Evaluation

Laboratory results will be graded using the NCI-CTCAE, version 4.03, except where common terminology criteria (CTC) grades are not available. Laboratory tests that are not part of the NCI-CTCAE grading system will be summarized using the normal / above normal limit / below normal limit categories, unless otherwise specified.

In this study, there are three categories of laboratory evaluations for safety entered into the database as described below:

- (1) Hematology and biochemistry parameters, assessed by the central laboratory:
 - The hematology laboratory panel includes the following: White blood cell count, red blood cell count, hemoglobin, hematocrit, mean corpuscular volume, mean corpuscular hemoglobin concentration, erythrocyte sedimentation rate, platelet count, neutrophils (absolute and percentage), lymphocytes (absolute and percentage), monocytes (absolute and percentage), eosinophils (absolute and percentage), basophils (absolute and percentage).
 - The biochemistry panel includes the following: Sodium, potassium, blood urea nitrogen, creatinine, alkaline phosphatase, alanine aminotransferase, aspartate aminotransferase, gamma-glutamyl transferase, lactate dehydrogenase, serum albumin, calcium, phosphate, glucose, creatine kinase, uric acid, total bilirubin, total serum protein, cholesterol, triglycerides, C-reactive protein, coagulation (activated partial thromboplastin time and prothrombin time).
- (2) Urinalysis will be assessed by the central laboratory and includes the following: Dipstick, including macroscopic appearance, bilirubin, blood, color, glucose, ketones, leukocyte esterase, nitrite, pH, protein, specific gravity, and urobilinogen. Full urinalysis (dipstick plus microscopic evaluation) at the Investigator's discretion only if warranted by an abnormal dipstick finding.

(3) Anti-nuclear antibody (ANA) and anti-double stranded deoxyribonucleic acid (dsDNA).

For category (1), absolute values and change from baseline will be summarized by visit and treatment arm. Absolute values will also be summarized overall, with percentage of subjects below lower limit / 10 and lower limit / 3, and above 10 x upper limit and 3 x upper limit. Boxplots will also be produced for absolute change from baseline, by visit and by treatment arm. Normal ranges will be provided by the central laboratory, and out of range flags will be calculated based on the normal ranges. Shift tables will be produced of the number of subjects with low, normal and high values based on normal ranges by visit and baseline for all parameters with normal ranges available. Laboratory values will also be summarized by worst on-treatment value and shift from baseline to worst on-treatment value, and by worst on-treatment NCI-CTCAE toxicity grade and shift from baseline to highest grade. For summaries of laboratory values, "on-treatment" will be defined as all available post-baseline values up to and including the Week 52/4-week safety follow-up safety visit or 28 days after the last dose of study drug, whichever occurs later. Direction of abnormality and NCI-CTCAE gradable parameters are presented in Appendix II: Direction of Abnormality for Worst On-treatment Values and NCI-CTCAE Gradable Parameters.

For category (2), absolute values and change from baseline will be summarized by visit and treatment arm. Shift tables by visit and baseline will be produced for parameters with categorical values.

For category (3), ANA and anti-dsDNA status will be listed and summarized.

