## **5.4 Criteria for Patient Withdrawal**

### **5.4.1 Withdrawal from Trial Therapy**

A patient will no longer receive the study medication in the event of any of the following circumstances:

- a. Any events that unacceptably endanger the safety of the patient, including but not limited to the following:
  - Use of prohibited treatment that in the opinion of the Investigator or Sponsor necessitates the patient treatment to be interrupted
  - Occurrence of an exclusion criterion that is clinically relevant and affects the patient's safety, if discontinuation is considered necessary by the Investigator and/or Sponsor
  - Anaphylactic or other serious allergic reactions
  - Development of active or latent TB
  - New or worsening symptoms of congestive heart failure
  - Biopsy confirmation of any malignancy other than non-melanoma skin cancer, such as basal cell carcinoma and squamous cell carcinoma.
  - Symptoms suggestive of lupus-like syndrome
  - Pregnancy
- b. Interruption of MTX more than twice in a period of 4 weeks, or for a period of interruption longer than 4 months.

- c. Noncompliance or protocol violations that in the opinion of the Investigator or Sponsor necessitates the patient being withdrawn. The decision to withdraw the patient should be taken in consultation with the Medical Monitor.
- d. Participation in any other trial during the duration of this trial.
- e. If the whole trial is discontinued prematurely.
- f. Lost to follow-up.

If a patient is lost to follow-up, every possible effort must be made by trial center personnel to contact the patient and determine the reason for discontinuation. The measures taken to follow-up must be documented. If a patient discontinues before completion of trial procedures, the reason for discontinuation must be documented in the CRF and source documents.

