#### Other Secondary Endpoints

- Safety
  - Occurrences of TEAEs and SAEs including and up to the 4-month Safety Evaluation visit (AEs will be recorded at each visit: screening, baseline [Week 0], and Weeks 2, 4, 8, 12, 24, 36, 48, and 52, and 4-week and 4-month Safety Follow-up)
  - Vital signs at screening, baseline and at Weeks, 2, 4, 8, 12, 24, 36, 48, and 52
  - Physical examination at screening, baseline and at Weeks 2, 4, 8, 12, 24, 36, 48, and 52
  - Hematology, urinalysis and biochemistry analysis at screening, baseline and at Weeks 2, 4, 12, 24, 36, 48, and 52
  - ANA and anti-dsDNA at baseline and at Weeks 24 and 52
  - 12-lead ECG at screening, Weeks 12, 24, and 52

- Immunogenicity
  - ADA to adalimumab and ADA titer including and up to Week 52
  - Neutralizing ADA to adalimumab including and up to Week 52
- Efficacy
  - ACR20 at Weeks 2, 4, 8, 24, and 52
  - ACR50 response rates at Weeks 2, 4, 8, 12, 24, and 52
  - ACR70 response rates at Weeks 2, 4, 8, 12, 24, and 52
  - Change from baseline in DAS28-ESR to Weeks 2, 4, 8, 12, 24, and 52
  - Proportion of patients with DAS28 low disease activity and remission at Weeks 2, 4, 8, 12, 24, and 52
  - Change from baseline in SDAI at Weeks 2, 4, 8, 12, 24, and 52
  - Change from baseline in CDAI at Weeks 2, 4, 8, 12, 24, and 52
  - ACR/EULAR Boolean remission rates at baseline, Weeks 2, 4, 8, 12, 24, and 52
- Quality of Life (QoL) and Physical Function
  - At baseline, then at Weeks 12, 24, and 52:
    - HAQ-DI - Health Assessment Questionnaire – Disability Index
    - SF-36 - 36-item Short-Form Health Survey
    - EQ-5D-5L - The EuroQoL-5D-5L dimension instrument
  - Injection site pain
    - Mean change in injection site pain on a VAS, evaluated during 3 (doses 3-5) administrations of IMP

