### 8.5.3.3 Analysis of Safety Endpoints

Safety endpoints below will be summarized by treatment group:

- Treatment-emergent AEs, SAEs, AESIs, and deaths
- Clinical laboratory values including hematology, chemistry, and urinalysis
- Vital signs
- Physical exam
- 12-lead ECG

Adverse events will be coded with the latest version of the Medical Dictionary for Regulatory Activities and summarized by treatment group overall, by severity, and by relationship to MSB11022-CCI [REDACTED] or Humira®.

The nature, severity and frequency of the adverse drug reactions in patients who received MSB11022-CCI [REDACTED] will be compared with those who receive Humira® to evaluate comparability of safety.

AEs and concomitant medications will be recorded at each visit: screening, baseline (Week 0), and Weeks 2, 4, 8, 12, 24, 36, 48, and 52.

Summary statistics will be used to present changes from baseline in continuous laboratory and vital sign variables.

Shift tables will be used to present changes in categorical laboratory variables.

All clinical laboratory data will be stored in the database in the units in which they were reported and using the laboratory reference ranges. Patient listings and summary statistics at each assessment time will be presented using the International System of Units (SI units). Laboratory data not reported in SI units will be converted to SI units before processing.

Safety endpoints will be analyzed using the safety analysis set.

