11.1 Descriptive Methods

Descriptive statistics for continuous data will include the following:

- Number of subjects with non-missing data (n)
- Number of subjects with missing data
- Mean, standard deviation (SD)
- Median, first and third quartiles (Q1 and Q3)
- Minimum and maximum
- 95% confidence interval (CI).

All statistics will be rounded according to Merck's Global Biostatistics Output Standards (GBSOS) Booklet (Version 4.0 or later), ie, percentages will be rounded to one decimal. The mean, median, Q1, Q3, and 95% CI will be presented with one additional decimal compared to the raw data; SD will be presented with two additional decimals compared to the raw data; and minimum and maximum will be presented with the same number of decimals as the raw data.

All data will be presented by nominal visit (including the safety follow-up visits – four weeks and four months after the last dose of IMP) and no visit windowing rules will be implemented. Data from unscheduled visits will be listed but will not be included in summaries presented by

visit. The exceptions will be in the calculation of the baseline values. Data from unscheduled visits will also be included in the calculation of the worst on-treatment values and grades.

Categorical data will be summarized by presenting the number of subjects with non-missing data (n), the number of subjects with missing data (missing), and the number and percentage of subjects in each category. Percentages will be based on the number of subjects with non-missing data in the analysis set of interest, unless otherwise specified.

Time to event variables will be summarized by presenting Kaplan Meier estimates and 95% CIs.

Change from baseline will be calculated as the post-baseline value minus the baseline value. Percent change from baseline is defined as (100 x (post-baseline – baseline) / baseline).

If all baseline values are missing for a particular variable, the change from baseline and percent change/percent improvement from baseline will not be calculated.

A 2-sided significance level of 5% will be used for all analyses. Two-sided 95% confidence intervals will be calculated.

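### SAP 16.3 plans no shift from baseline for ANA and anti-dsDNA, so its tables will not separate newly positive patients from those positive before dosing

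*SAP*

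**What the plan says.** Protocol 8.3.2 lists these antibodies among the other secondary safety endpoints: "ANA and anti-dsDNA at baseline and at Weeks 24 and 52". Table 1 also schedules them at the early termination (ET) visit and the 4-week safety follow-up. Protocol Table 3 places them among the clinical laboratory assessments, under its last row of other tests. For the analysis, Protocol 8.5.3.3 states: "Shift tables will be used to present changes in categorical laboratory variables".

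SAP 16.3 sorts the safety laboratory data into three categories:

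- Category (1), haematology and biochemistry, has shift tables by visit and more: "Laboratory values will also be summarized by worst on-treatment value and shift from baseline to worst on-treatment value".
- Category (2), urinalysis: "Shift tables by visit and baseline will be produced for parameters with categorical values".
- Category (3), ANA and anti-dsDNA: "For category (3), ANA and anti-dsDNA status will be listed and summarized".

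No other SAP section defines a shift, a treatment-emergent positive result or a baseline-negative denominator for these antibodies. SAP section 9, on changes to the protocol's planned analyses, is marked not applicable.

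**The concern.** For a comparative safety objective, the useful question about an autoantibody is how many patients acquire it on drug in each arm. That needs each patient's later status set against the same patient's baseline status. The category (3) sentence does not ask for this, although its two neighbours do and the protocol's general rule would.

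Baseline status matters because entry does not depend on it. The exclusion criteria in Protocol 5.3.2 rule out other systemic autoimmune diseases (secondary Sjögren's syndrome is allowed), but they do not mention ANA or anti-dsDNA results, and the first sample is drawn on Day 1. QuantiFERON is different: a positive result at screening excludes the patient, so a later positive is new without any cross-tabulation.

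At stake is a readable answer on one secondary safety endpoint. The primary endpoint is not affected.

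**Working it through.** The documents give no figure for ANA or anti-dsDNA, so there is nothing to reproduce. The check has a textual part and an illustration.

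**Text**

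1. The SAP reports these antibodies as a status, which is a categorical laboratory variable. Read plainly, the shift-table rule in Protocol 8.5.3.3 covers it.
2. The shift tables in SAP 16.3 are tied to categories (1) and (2). Category (3) has its own sentence, which names no baseline comparison.
3. SAP 11.1 adds a general rule: "All data will be presented by nominal visit". SAP section 11 presents summaries by arm. The likely output is therefore the number positive at baseline, Week 24, Week 52 and follow-up, by arm. These are marginal counts.

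**Do two marginal counts identify new positives?** Let N be the patients in an arm, b the share positive at baseline, q the share positive at Week 52, and r the share of baseline positives who revert to negative.

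New positives = N × [q − b(1 − r)]

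N = 130 comes from Protocol 8.1. The values of b, q and r are assumptions. With b = 0.30 and q = 0.40, 39 patients are positive at baseline and 52 at Week 52:

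- r = 0: 52 − 39 = 13 new positives, or 13/91 = 14% of baseline negatives.
- r = 0.30: 52 − 27.3 = 24.7, about 25 new positives, or 27% of baseline negatives.

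The by-visit table is identical in the two cases, while the number of conversions nearly doubles.

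**How much of the later count is old?** With no reversion and new positivity c among baseline negatives, the share of Week 52 positives who were positive before dosing is b / [b + (1 − b)c]:

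| b | c = 0.05 | c = 0.10 | c = 0.20 |
|---|---|---|---|
| 0.10 | 69% | 53% | 36% |
| 0.20 | 83% | 71% | 56% |
| 0.30 | 90% | 81% | 68% |
| 0.40 | 93% | 87% | 77% |

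**Dilution of the arm difference.** With equal b in both arms and no reversion, the status difference equals (1 − b) × (difference in c). Assume c is 10% in one arm and 20% in the other. The 95% half-width is 1.96 × √[p₁(1 − p₁)/n + p₂(1 − p₂)/n], with n = 130 for status and n = 130(1 − b) for conversion. The ratio is the difference divided by its standard error.

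| b | Status: difference ± half-width (points) | Ratio | Conversion: difference ± half-width (points) | Ratio |
|---|---|---|---|---|
| 0.20 | 8 ± 11 | 1.39 | 10 ± 10 | 2.04 |
| 0.30 | 7 ± 12 | 1.15 | 10 ± 10 | 1.91 |
| 0.40 | 6 ± 12 | 0.97 | 10 ± 11 | 1.77 |

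The protocol aims for 200 patients at Week 52. With 100 per arm, every ratio is multiplied by √(100/130) = 0.877. The status ratios become 1.22, 1.01 and 0.85, and the conversion ratios 1.79, 1.67 and 1.55.

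**The case against.** The strongest defence is that the category (3) sentence is terse rather than deficient. A summary of status does not exclude a shift table, the SAP says it is based on Protocol section 8, and the output shells, which are not in the documents, may contain one. It can also be argued that Protocol 8.5.3.3 means haematology, chemistry and urinalysis, the groups it names, and so never promised a shift for ANA. These arguments soften any charge of contradiction. They do not remove the gap. The protocol's list is introduced as inclusive, Table 3 counts these antibodies as clinical laboratory assessments, and a SAP that spells out shifts for two categories should not leave the third to be guessed.

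It is also fair to say that little information is lost. Baseline prevalence would appear beside the later visits, and SAP 11.3 lists all data, so conversions can be traced patient by patient. That stands, but reading listings for about 260 patients is not a pre-specified summary.

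Four stronger readings are tempting, and the documents do not support them:

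- *Patients who stop early would appear only in the listings.* ET and the 4-week follow-up are scheduled visits for these antibodies. SAP 11.1 includes the safety follow-up visits in by-visit presentations and leaves out only unscheduled ones, and the category (3) sentence has no visit restriction.
- *The status comparison is invalid.* The arms are randomised, so the difference in post-baseline status is a fair comparison. It is less sensitive to new antibody formation.
- *The antibodies were collected as lupus markers.* Protocol 5.4.1 lists "Symptoms suggestive of lupus-like syndrome" as a reason to stop study medication, but no section ties the serology to that risk. The link is a reasonable inference, and the point does not need it.
- *The trial would miss a real difference without the shift table.* The ratios above rest on assumed rates, including a doubling between arms, no reversion and complete data. With 100 per arm, neither scale excludes zero in any of the three scenarios. The study is descriptive in any case.

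**Conclusion.** The point holds as an omission that is cheap to repair. SAP 16.3 does not state, for ANA and anti-dsDNA, the shift table that Protocol 8.5.3.3 gives for categorical laboratory variables and that the other laboratory categories receive, and no change from the protocol is declared. By-visit status counts cannot identify new positivity, because baseline-positive patients can be enrolled and reversion is possible. This follows from the design and needs no assumed rate.

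The size does depend on assumed rates. Over the ranges shown, between 36% and 93% of Week 52 positives would have been positive before dosing, and a 10-point difference in conversion would appear as 6 to 8 points in status. These figures assume no reversion and equal baseline positivity in the arms, and they are illustrations only.

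**What to change.** In SAP 16.3, replace the category (3) sentence with wording such as:

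*For ANA and anti-dsDNA separately, status will be listed, and a shift table by treatment arm will cross-tabulate baseline status (negative, positive, missing) against status at each scheduled post-baseline visit and against any positive post-baseline result, including ET and unscheduled results. The number and percentage of baseline-negative subjects who become positive will be given by arm, with an exact (Clopper-Pearson) 95% CI.*

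The shift table alone would satisfy Protocol 8.5.3.3. The CI uses the method already planned for the primary endpoint in SAP 15.1. A between-arm CI is optional, since SAP 16.3 plans none for any other laboratory variable. Using unscheduled results in the any-positive column matches how SAP 11.1 treats worst on-treatment values.

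The cost is a change of SAP wording and one or two tables from data already collected. No visit, sample or clinical rule changes. If the tables are added after database lock, SAP section 5 requires the clinical study report to identify them as unplanned.

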16.4 Vital Signs

Absolute values and change from baseline in blood pressure, heart rate, weight, body temperature and respiratory rate will be summarized by visit and treatment arm. The maximum change from baseline will be listed for each vital sign parameter for each subject.

Temperature will be presented in degrees Celsius (°C). The conversion factor used will be:

• Temp ($^{\circ}$ C) = (5/9)*(Temp($^{\circ}$ F) - 32)

See Section 12.4 for height and weight conversions.

For vital signs that have been measured twice at the same visit the average value at the visit will be calculated and used. (All individual values per visit will be listed.) Shift tables (including number of subjects and percentages) of vital signs (systolic blood pressure, diastolic blood pressure, pulse rate, body temperature, and respiratory rate), displaying baseline value versus worst on-treatment value will be provided for both increases and decreases. For summaries of vital signs, "on-treatment" will be defined as all available post-baseline values up to and including the Week 52/4-week safety follow-up safety visit or 28 days after the last dose of study drug, whichever occurs later.

The following parameter categories will be used for the vital signs shift tables:

Parameter	Baseline categories	Post-baseline categories
Systolic blood pressure (SBP)	< 140 / ≥ 140 mmHg	Absolute change of: ≤ 0 / > 0 - ≤ 20 / > 20 - ≤ 40 / > 40 mmHg
Diastolic blood pressure (DBP)	≤ 90 / > 90 mmHg	Absolute change of: $\leq 0 / > 0 - \leq 20 / > 20 - \leq 40 / > 40 \text{ mmHg}$
Heart rate	< 100 / ≥ 100 bpm	Absolute change of: $\leq 0 / > 0 - \leq 20 / > 20 - \leq 40 / > 40$ bpm
Temperature	< 37°C / ≥ 37 - < 38°C / ≥ 38 - < 39°C / ≥ 39 - <40°C / ≥ 40°C	Absolute change of: $\leq 1 / > 1 - \leq 2 / > 2 - \leq 3 / > 3^{\circ}C$
Respiratory rate	< 20 / ≥ 20 bpm	≤ 5 / > 5 - ≤ 10 / > 10

16.5 Other Safety or Tolerability Evaluations

16.5.1 ECGs

Summary results will be presented for Week 12, 24 and 52. Shifts from baseline in ECG results will be presented by treatment arm. For summaries, "on-treatment" will be defined as all available post-baseline values up to and including the Week 52/4-week safety follow-up safety visit or 28 days after the last dose of study drug, whichever occurs later.

